All vasopressor therapies used in critically ill patients have a variety of side effects. Angiotensin II, when the trial data was reviewed by the FDA, was determined to have a higher rate of thrombotic risk compared to placebo, and thus was labeled with a warning regarding this high rate of thrombotic and thromboembolic risk (13% vs. 5%) (1). This was much higher than the rate of 1.8% deep vein thrombosis reported by the pivotal phase III trial (2). Critically ill patients are at very high risk for venous thromboembolism, with some estimates of the incidence as high as 37.2% in patients with sepsis despite prophylaxis (3). When additional information is requested from the manufacturer, the discrepancy between the pivotal trial and package insert is explained as a distinction in the designation of serious adverse event (SAE) and adverse event (AE). In the pivotal phase III trial, only SAEs that occurred more frequently than 1% (a subset of all thromboembolic events) were reported whereas in the package insert, all thromboembolic events were merged into a single group that included any thromboembolic event, both serious and non-serious. A majority of patients in this pivotal trial were receiving VTE prophylaxis, but very often, critically ill patients have contraindications to pharmacologic prophylaxis, so not all patients were receiving. In this communication to the manufacturer, there was a trend toward fewer thromboembolic AEs when patients were receiving VTE prophylaxis. Recently, a multicenter observational study of real-world use has reported venous thromboembolism rates similar to those in the pivotal phase III trial (2/133 or 1.5% in this study) (4). Taken together, these data are consistent with the FDA's recommendation to prescribe VTE prophylaxis concurrently (although it is not a contraindication to prescribe if VTE prophylaxis is contraindicated) (1). However, as noted, many patients in the ICU have temporary contraindications to such, which is why standard of care is to address pharmacologic VTE prophylaxis daily on multidisciplinary rounds using a checklist-based system (and if remains contraindicated non-pharmacologic devices are applied to the patient). Given the inherent risks of a patient in septic shock, the benefits of prescribing this medication may outweigh the risks of thrombosis, even in patients not receiving pharmacologic prophylaxis.

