Community-Based Participatory Research: If you are conducting [community-based participatory research \(CBPR\)](#), describe strategies for involvement of community members in the design and implementation of the study, and dissemination of results from the study.

Research Repositories: If the purpose of this submission is to establish a Research Repository (bank, registry) indicate whether the material you plan to collect would or would not be available from a commercial supplier, clinical lab, or established IRB approved research repository. Provide scientific justification for establishment of an additional repository collecting duplicate material. Describe the repository design and operating procedures. For relevant information to include, see the UK Research Biospecimen Bank Guidance [\[PDF\]](#) or the UK Research Registry Guidance [\[PDF\]](#)

This will be a pre-post study built to replicate the introduction of angiotensin II into the clinical practice at UK HealthCare as outlined in the study protocol. 10 patients will be recruited, who receive normal standard of care, and consented to obtain plasma renin levels and biomarkers of renal function (three blood draws). After 10 patients, the next 20 patients meeting eligibility criteria will receive angiotensin II, they will also have blood drawn (four blood draws) to evaluate renin and renal biomarker response to angiotensin II.

Attachments

[Back to Top](#)

Study Population: Describe the characteristics of the subject population, such as anticipated number, age range, gender, ethnic background and health status. Identify the criteria for inclusion and exclusion. Explain the rationale for the use of special classes such as fetuses, pregnant women, children, institutionalized, adults with impaired consent capacity, prisoners, economically or educationally disadvantaged persons or others who are likely to be vulnerable.

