Intervention group (n=20): Standard of care will be followed for the management of septic shock. At which point the patient meets the inclusion criteria of the study, the patient's treating physician will be approached about the opportunity to offer angiotensin II to the patient. If the treatment team wishes to pursue, the patient or their LAR will be approached for written informed consent. Angiotensin II will be dosed per the protocol, and the patient will receive blood draw at the time they meet inclusion criteria (time T), 3 hours later (T+3), and 24 hours from angiotensin II initiation (T+24 hours), and when the patient no longer requires vasopressor agents to support their blood pressure (defined as off of vasopressors for at least 4 hours). If the patient ceases vasopressor agents within 12 hours of the third blood draw, the fourth and final blood draw will not be collected. All other aspects of the patient's care will be per the standard of care in the medical intensive care unit. Blood samples will be centrifuged, plasma extracted, and stored at -80 C. Commercial ELISAs will be used for analysis of renin and renal biomarkers (cystatin C, NGAL, renin, angiotensin II, angiotensin 1-7). COVID specification. Testing positive is a known exclusion criteria for the study. If a patient has results when evaluated for the study, this will be straightforward. However, if the test is pending while the patient is eligible for study entry, this will not make the patient ineligible for the study. If, in the opinion of the attending physician, COVID-19 is highly likely the patient will not be approached for informed consent. Otherwise, if COVID-19 test is pending, the patient or LAR will be approached for informed consent. If the test results as negative, study procedures will be performed as planned. If the test returns positive, the patient will be informed and dropped from the study. We will use their baseline information collected up to that point, but they will no longer receive blood draws or study medication (angiotensin II) once confirmed COVID positive. A case series of angiotensin II has been published in COVID 19

patients, and given the acuity of the disease state in question, it would not be appropriate to wait for a negative COVID test in our judgement.

Attachments

Data Collection: List the data or attach a list of the data to be collected about or from each subject (e.g. interview script, survey tool, data collection form for existing data).

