Following enrollment of the 10 patients in the control arm and 10 patients in the angiotensin II arm (i.e. half of the 20 patients that will ultimately receive the drug), we will evaluate the risk of venous thromboembolism and any additional reported thrombotic reports from the 10 patients that have received angiotensin II. Groups will be compared using a Fisher's exact test given the small sample size. Given the concern for safety, if the p-value is 0.15 or less with increased thrombotic events in the angiotensin II group, the open-label study will be stopped. For example, assuming a baseline rate of thrombotic events of 1/10 (10%) in the control arm, if 5/10 patients in the angiotensin II group (50%) experienced a thrombotic event, a Fisher exact test yields p=0.141 and the open-label use of angiotensin II would be stopped due to concern for safety. If thrombotic event differences do not meet this threshold, we will continue with the enrollment of an additional 10 patients to meet the 20 patient enrollment set.

[Back to Top](#)

Subject Complaints: Describe procedures (other than information provided in consent document) for handling subject complaints or requests for information about the research. The procedures should offer a safe, confidential, and reliable channel for current, prospective, or past research subjects (or their designated representative) permitting them to discuss problems, concerns and questions, or obtain information.

Subject complaints will be directed to the primary investigator, who will contact the subjects to discuss their concerns, including potential withdraw from the study or use of their information. If a subject has any concerns or questions about his/her rights as a volunteer in this research, they will be advised to contact staff in the Office of Research Integrity (ORI).

Does your research involve **Non-English Speaking Subjects or Subjects from a Foreign Culture?**

Yes No

—Non-English Speaking Subjects or Subjects from a Foreign Culture—

Describe how information about the study will be communicated to potential subjects appropriate for their culture, and if necessary, how new information about the research may be relayed to subjects during the study.

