[To view what materials are currently attached to your application, go to "Application Links" in the menu bar on the left and click "All Attachments".]

Attachments

Attach Type	File Name
AddInfoConsiderations	57411 [name].pdf

Statistical Analysis

Continuous data will be described using medians and interquartile ranges. Discrete data will be described as counts and percentages. Changes in biomarker measurements will be calculated by subtracting the biomarker measurement at subsequent timepoint from the baseline biomarker measurement at enrollment. Assuming non-normal distributions of biomarker measurements with extreme elevations as well as skewness of the data for lengths of stay, continuous variables will be compared using the Mann-Whitney U test while discrete data will be compared between groups using chi-squared or Fisher's exact test as appropriate. A p-value <0.05 will be considered statistically significant.

Interim Analysis

Following enrollment of the 10 patients in the control arm and 10 patients in the angiotensin II arm (i.e. half of the 20 patients that will ultimately receive the drug), we will evaluate the risk of venous thromboembolism and any additional reported thrombotic reports from the 10 patients that have received angiotensin II. Groups will be compared using a Fisher's exact test given the small sample size. Given the concern for safety, if the p-value is 0.15 or less with increased thrombotic events in the angiotensin II group, the open-label study will be stopped. For example, assuming a baseline rate of thrombotic events of 1/10 (10%) in the control arm, if 5/10 patients in the angiotensin II group (50%) experienced a thrombotic event, a Fisher exact test yields $p=0.141$ and the open-label use of angiotensin II would be stopped due to concern for safety. If thrombotic event differences do not meet this threshold, we will continue with the enrollment of an additional 10 patients to meet the 20 patient enrollment set.

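### Once the control thrombosis count is closed, the stopping rule is a fixed event count, yet it is read only after the tenth angiotensin II patient (minor; inexpensive to improve)

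*Combined protocol and SAP*

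**What the plan says.** Study Design sets the order of enrolment. Ten control patients come first, and "After 10 patients, the next 20 patients meeting eligibility criteria will receive angiotensin II".

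Data and Safety Monitoring and the Interim Analysis section give the same safety rule. There is one comparison, "Following enrollment of the 10 patients in the control arm and 10 patients in the angiotensin II arm". It covers venous thromboembolism and "any additional reported thrombotic reports from the 10 patients that have received angiotensin II". The test is named ("Groups will be compared using a Fisher's exact test given the small sample size") but its side is not. The decision is that "if the p-value is 0.15 or less with increased thrombotic events in the angiotensin II group, the open-label study will be stopped"; otherwise 10 more patients are enrolled on the drug. One example is worked, 5/10 against 1/10: "a Fisher exact test yields p=0.141 and the open-label use of angiotensin II would be stopped due to concern for safety".

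Neither section gives a window for counting thrombotic events, a full list of results that would stop the study, or a reading of the count before the tenth treated patient. Data Collection lists venous thromboembolism among the side effects to be monitored, and Safety Precautions refers to routine intensive care monitoring. Neither is tied to a stopping decision.

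**The concern.** Because the controls are enrolled first, their event count can be known while angiotensin II patients are still being enrolled. With that count fixed and 10 patients per arm, the p-value depends only on how many angiotensin II patients have an event. That number can rise as patients are added but cannot fall. If it reaches the stopping value at, say, the seventh patient, patients 8 to 10 cannot change the result of the look. As written, they are still enrolled before the rule is read.

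This is the only quantitative safety stop in the visible text, and Background reports a labelled thrombosis warning for the drug (13% vs 5%). At stake is avoidable exposure of a few patients in exactly those trials where the rule is needed.

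**Working it through.** **Inputs.** 10 per arm, p ≤ 0.15, angiotensin II excess required (Interim Analysis). Controls first (Study Design). Control vs angiotensin II rates: 5% vs 13% (label rates in Background); 10% vs 50% (the plan's example proportions, taken here as true rates); 10% vs 30% (assumed, as an intermediate case).

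**1. The plan's own figure.** Fisher's exact test on 5/10 vs 1/10 gives 0.1409 two-sided and 0.0704 one-sided. The stated 0.141 is the two-sided value, so the two-sided rule is used below.

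**2. The boundary.** For each control count c, take the smallest angiotensin II count b above c with two-sided p ≤ 0.15:

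| Control events c | b | p at b | p at b − 1 | Most patients enrolled after b is reached (10 − b) |
|---|---|---|---|---|
| 0 | 4 | 0.087 | 0.211 | 6 |
| 1 | 5 | 0.141 | 0.303 | 5 |
| 2 | 7 | 0.070 | 0.170 | 3 |
| 3 | 8 | 0.070 | 0.179 | 2 |
| 4 | 9 | 0.057 | 0.170 | 1 |
| 5 | 9 | 0.141 | 0.350 | 1 |
| 6 | 10 | 0.087 | 0.303 | 0 |
| 7 or more | none | – | – | – |

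For each c, every count from b to 10 also meets the rule, so further events cannot undo a stop.

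**3. When the boundary is reached.** With event rate p on angiotensin II, the b-th affected patient is patient k with probability C(k−1, b−1) p^b (1−p)^(k−b), for k = b to 10. Summed over k this equals P(at least b events in 10). Reading the count early therefore gives the same P(stop) as reading it at 10. The number enrolled afterwards is 10 − k.

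For c = 1, b = 5, p = 0.5, the probabilities for k = 5 to 10 are 0.031, 0.078, 0.117, 0.137, 0.137 and 0.123. They sum to P(stop) = 0.623. The boundary is reached by patient 9 with probability 0.500, which is 0.500/0.623 = 80% of stops. The sum of (10 − k) times each probability is 1.23, so the mean number enrolled afterwards, given a stop, is 1.23/0.623 = 2.0.

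**4. Averaged over the control count,** with c distributed Binomial(10, control rate):

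| Control vs angiotensin II | P(stop) | Stops settled before patient 10 | Patients enrolled afterwards, all trials | Given a stop | Given a stop, one-patient lag |
|---|---|---|---|---|---|
| 5% vs 13% | 2.0% | 66% | 0.03 | 1.4 | 0.8 |
| 10% vs 30% | 18% | 73% | 0.3 | 1.8 | 1.0 |
| 10% vs 50% | 57% | 83% | 1.4 | 2.4 | 1.6 |

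The all-trials column is P(stop) times the conditional mean; for example, 0.0204 × 1.43 = 0.03. The lag column assumes one more patient is enrolled before the event is recognised.

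**5. False stops.** With equal rates in both arms, P(stop) is 0.5% at 10% and 3.0% at 37.2%. Its maximum is 3.1%, at a common rate of about 31.5%. These values are the same for either way of reading the rule.

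**6. Dependence on the control count.** At 5/10 vs 1/10 the rule stops (p = 0.141). If one control has a late event, 5/10 vs 2/10 gives p = 0.350 and it does not. The boundary moves from 4 to 5 when c goes from 0 to 1, and from 5 to 7 when c goes from 1 to 2.

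**The case against.** The strongest objection is to the word certain. A reader might infer that the stopping number is fixed as soon as the tenth control is enrolled. The documents do not support that: Study Design orders enrolment only, and no event window is given. A control still under observation can have an event and raise the boundary, and a reported event may later be refuted. This objection stands, so the point holds only after control follow-up is closed and for confirmed patients with an event.

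The second objection is size. At the label rates the boundary is met before the tenth patient in 1.3% of trials, and the saving is 0.03 patients per trial. The 10% vs 50% case turns a worked p-value into assumed true rates. This stands too, and is why the point is minor.

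Third, a reader might infer that the rule is invalid or that earlier action is ruled out. Neither follows. One look at half of the treated group is a coherent design, the test is valid, and nothing forbids an investigator from acting on judgement. The point concerns the written rule alone. The detailed protocol is listed as an attachment but not shown, and the check marks against the monitoring board and monitoring plan under Research Attributes cannot be read. A running review may exist there.

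The worry that repeated reading inflates error does not stand. The boundary for 10 vs 10 is checked early; no new Fisher test is run at each sample size.

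**Conclusion.** The point holds as an inexpensive improvement: minor, with moderate confidence. Once the control count is closed, the plan's rule is a known number of affected angiotensin II patients, and waiting for the tenth patient can add enrolments that cannot alter the decision. The limit is 6 such patients with no control events and 5 with one. The gain is concentrated in the trials that stop and is close to nil on average at the label rates. The timing figures assume independent events at constant rates and, except in the lag column, that each event is known before the next enrolment.

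The unstated side of the test and the handling of patients dropped after a positive COVID-19 test are supporting details, not separate defects. The worked example already implies a two-sided test, and the wording about patients who have received the drug already implies that dropped patients stay in the count.

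**What to change.** In Data and Safety Monitoring and in Interim Analysis, keep the Fisher test, the 0.15 threshold and the direction condition, and add the following:

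1. The p-value is two-sided, as the example implies.
2. The full boundary at 10 vs 10: 0, 1, 2, 3, 4, 5, 6 control events require at least 4, 5, 7, 8, 9, 9, 10 angiotensin II patients with an event; no stop at 7 or more. Its stopping probabilities can be given beside it.
3. One thrombotic event definition and one window for both arms, counting confirmed patients with an event. A patient who received angiotensin II and is later dropped stays in the count.
4. Once the control count is closed, check the angiotensin II count against the boundary after each reported event and apply the existing rule when it is met. Until then the boundary is provisional, because a late control event raises it.
5. Keep the look after the tenth patient for the decision to continue.

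The cost is wording and one running tally in a single-site, open-label study. A trial that stops early would also have fewer than 10 treated patients for the renin and renal biomarker comparison. Given the closed control count, which trials stop and how often a stop is false do not change. No new threshold or clinical rule is proposed.
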